3.5.1. Data Analysis

The pharmacometric and statistical analyses of the data obtained from this study will be conducted by the investigators and study statistician.

3.5.2. Variables and time points

Pharmacodynamics (Primary Variable): Glucose infusion rate during the last 2 hours (hours 7-9) of infusion of exendin-(9-39) *versus* vehicle is the primary pharmacodynamic variable of interest, although blood glucose measurements over time will be utilized in exploratory PK/PD analyses.

Pharmacokinetics (Primary Variables): The pharmacokinetic variables of interest include $AUC_{0-\infty}$, AUC_{0-t} , maximal concentration (C_{max}), time to maximal

concentration (T_{max}), concentration at end of infusion (C_{eoi}), steady state volume of distribution (V_{ss}), clearance (CL) and half-life ($t_{1/2}$) of exendin-(9-39). These will be derived through both non-compartmental and model-based methods.

Safety (Secondary Variables): Primary safety endpoints will include all types of adverse experiences, in addition to laboratory safety tests (hematology, chemistry, and urinalysis). 12-lead electrocardiograms (ECGs), vital signs and physical examinations will also be recorded.

Secondary Variables: Plasma insulin, blood glucose and betahydroxybutyrate levels.

3.5.3. Approach to analysis

The following populations are defined for the analysis and reporting of data.

All Subjects as Treated (AST): All subjects who received any dose of the investigational drug. This population will be used for assessment of safety and tolerability.

Per-Protocol (PP): All subjects who received protocol procedures sufficiently to ensure that these data will be likely to exhibit the effects of treatment, according to the underlying scientific model.

3.5.4. Statistical Methods

Analysis Overview: Each subject will undergo two experiments (i.e., either infusion of exendin-(9-39) or infusion of vehicle in random order. A two-treatment, two-period crossover design will be employed, with two sequence groups (i.e., vehicle infusion first followed by exendin-(9-39) infusion vs. exendin-(9-39) infusion first followed by vehicle infusion). Subjects will be randomly assigned to one or the other of the two sequence groups. The primary aim of the study is to evaluate the effect of exendin-(9-39) vs. vehicle on glucose infusion rate in subjects with congenital hyperinsulinism, and to measure PK parameters for exendin-(9-39), and PK/PD relationships between glucose infusion rate, blood glucose and exendin-(9-39) exposure. Descriptive statistics will be used to characterize demographic, baseline, and outcome measures in subjects. Means, SDs, 95% confidence intervals (CIs), medians, and minimum and maximum values will be tabulated and reported for all continuous variables, by infusion condition. Histograms will be used to determine extent of skewness, and transformations (e.g. logarithmic) will be considered for seriously skewed data. Frequency counts and percentages will be used for categorical variables (e.g., gender, race, adverse events).

Pharmacodynamics: To assess the effect of exendin-(9-39) on glucose infusion rate, glucose infusion rate (GIR) over the last 2 hours of the treatment period will be calculated by adding the total amount of intravenous glucose (in mg) received over 2 hours divided by the weight in Kg and by time (120 min) during infusion of vehicle and exendin-(9-39). Comparison between the two infusions of GIR will be made using the linear mixed effects models. Similarly, the plasma concentration of insulin, glucose and betahydroxybutyrate will be analyzed as above. Each of the outcome parameters will be analyzed separately using linear mixed effects

models (92), which are ideally suited for the cross-over design, as this design includes both fixed effects (treatment, period, carry-over) and random effects (the subjects). Moreover, software for linear mixed models (e.g., SAS proc MIXED) allows flexible modeling of the covariance structure, deals with unbalanced or missing data, and allows use of covariates that change both at the within and among-individual level.

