3.3. Study Population

Subjects will be recruited from patients referred to the Hyperinsulinism Center at The Children's Hospital of Philadelphia, the largest center in the USA, with approximately 30 referrals/year of children with medically-unresponsive hyperinsulinism and an equal number of children with medically-responsive hyperinsulinism. Three hundred and sixty one pancreatectomies have been performed in children with congenital hyperinsulinism within the last 16 years at this center. We plan to enroll approximately 20 additional subjects, beyond the 9 subjects already enrolled up through Amendment 6, making a total number of approximately 30 subjects for about 27 evaluable subjects and to include at least some subjects with diffuse disease.

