14. Determination of plasma insulin, blood glucose, and betahydroxybutyrate levels: Venous samples for determination of plasma insulin and plasma glucose will be obtained at 0, 1, 5 and 9 hours during the study period. Betahydroxybutyrate will be obtained hourly by heel stick during the study period. For subjects in whom the dextrose infusion has been discontinued by the end of the study infusion betahydroxybutyrate will be obtained every hour until 3 hours post-dose (or when blood glucose \leq 70 mg/dL, whichever comes first). In these subjects an additional sample will be obtained at the end of 3 hours (or when blood glucose $<$ 70 mg/dL, whichever comes first) for plasma glucose and insulin. Should there be

difficulty in establishing peripheral blood drawing lines to obtain samples of the secondary outcome variables, (Insulin, exendin-(9-39) levels) the study will proceed with collection of the primary outcome variable only (glucose infusion rate). Capillary and venous blood glucose will be measured using the Nova StatStrip point-of-care glucose monitor (Nova Biomedical Corporation, Waltham, MA, USA). Betahydroxybutyrate will be measured at the bedside using a ketone meter (PrecisionXtra, Abbott Laboratories). Blood samples for plasma glucose, insulin and betahydroxybutyrate levels will be sent to the hospital chemistry laboratory for processing.

3.5. Sample Size and Data Analysis.

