The goal of this study is to find the intravenous dose of exendin-(9-39) (and the plasma concentration) that is necessary to completely abolish the need for exogenous glucose administration to maintain normal blood glucose in children with congenital hyperinsulinism. The sample size of three for each dosing regimen is a sample of convenience and not based on statistical considerations. However, we offer the following considerations based on our previous studies: for the first 9 subjects studied under this protocol the mean \pm standard deviation (SD) baseline glucose infusion rate (GIR) was 13.2 ± 4.8 mg/kg/min. Our hypothesis is that exendin-(9-39) will decrease the glucose infusion rate required to maintain blood glucose > 70 mg/dL. A paired test is called for to compare the two conditions – exendin-(9-39) and vehicle; however, since we do not actually know the SD of differences, our sample size calculation is based on the more conservative t-test for independent samples, and we use the SD of 4.8 as an estimate of the common SD; using a two group t-test with a 0.05 two-sided significance level.

Reduction in GIR	Sample size for 80% power	Sample size for 90% power
25%	34	45
50%	9	12
100%	3	4

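### The one-value-per-day GIR model is applied to serially sampled insulin and betahydroxybutyrate without saying how the samples, or the 0-h value, enter it

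*Combined protocol and SAP*

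**What the plan says.** **Model.** Section 3.5.4 (Pharmacodynamics) compares GIR between infusions with a linear mixed model. GIR is the glucose given over the last two hours divided by weight and 120 minutes, so each infant-day gives one value. Mixed models are said to suit the crossover "as this design includes both fixed effects (treatment, period, carry-over) and random effects (the subjects"). No other model terms are named. A further remark notes that the software can handle various covariance patterns and covariates that change within an infant, but it selects none.

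**Outcomes sent to it.** "Similarly, the plasma concentration of insulin, glucose and betahydroxybutyrate will be analyzed as above".

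**Sampling.** Section 3.4, item 14, sets the schedule. For the venous draws that serve both insulin and glucose, samples "will be obtained at 0, 1, 5 and 9 hours during the study period". The ketone measurements are more frequent, one each hour by heel stick. Infants off dextrose at the end of the infusion have further samples, up to three hours later.

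**Time points.** Section 2.1 fixes plasma glucose at one hour into the infusion as a secondary outcome, but gives no time for insulin or betahydroxybutyrate. Section 3.5.2, which is headed as covering time points, gives a window for GIR only and does not repeat the 1-h definition for glucose.

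**The concern.** A subject random effect is enough when each infant gives one value per day. With four or ten values per day, two questions arise that the plan leaves open.

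- **The 0-h sample.** Section 3.2 places a 3-hour run-in before treatment, so the 0-h value cannot show a drug effect on either day. In a model without a time term it would still be averaged into that day's treatment.
- **Correlation within a day.** A random subject intercept allows for correlation among all of an infant's samples. It does not allow for extra similarity among samples from the same day. Treatment changes only between days, so that extra similarity belongs in its standard error.

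Suppressed insulin is part of the hypothesis in section 2.1, so the insulin estimate matters for interpretation. As the plan stands, two competent analysts could report different estimates and p-values from the same data.

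**Working it through.** **1. The plan's own figure.** The only calculation in section 3.5 is the GIR sample-size table. It uses "13.2 ± 4.8 mg/kg/min" for baseline GIR, "using a two group t-test with a 0.05 two-sided significance level". With n per group = 2(z₀.₉₇₅ + z_power)²(4.8/δ)² and δ = 3.3, 6.6 and 13.2:

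| Reduction | Stated (80%/90%) | Normal formula | t-test |
|---|---|---|---|
| 25% | 34/45 | 34/45 | 35/46 |
| 50% | 9/12 | 9/12 | 10/13 |
| 100% | 3/4 | 3/3 | 4/5 |

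The table reproduces to within 1. It concerns GIR only; nothing comparable is given for insulin, glucose or betahydroxybutyrate.

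**2. Inputs for this point.** Samples per day m = 4 for insulin (0, 1, 5, 9 h) and m = 10 for betahydroxybutyrate (an assumption: hourly, 0 to 9 h inclusive). Section 3.3 expects "approximately 30 subjects for about 27 evaluable subjects"; n = 20 is shown below, and n = 6, 14 and 27 are close. Residual variance σ² is set to 1. Infant-by-day variance τ² of 0, 0.25, 0.5 and 1.0 and subject variance ω² of 0.5 to 2 are assumptions, because the documents give neither.

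**3. Dilution.** Without a time term, the treatment estimate compares day means over all m samples. An effect δ present at m − 1 of them has expected estimate δ(m − 1)/m:

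- insulin: 3/4, a loss of 25%;
- betahydroxybutyrate: 9/10, a loss of 10%.

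In simulation without carry-over, a true 0.60 came out at about 0.45 and 0.54. For four samples the loss was the same with carry-over in the model. No variance assumption is involved.

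**4. Type I error, carry-over dropped** (treatment and period fixed, random subject, independent residuals). The treatment contrast varies in proportion to L = σ² + mτ². The model instead uses a residual mean square with expectation [(n−2)L + 2n(m−1)σ²] / [(n−2) + 2n(m−1)].

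Example: n = 20, m = 4, τ² = 0.25. L = 2 and the expected mean square is (18×2 + 120)/138 = 1.13. The variance is understated by 2/1.13 = 1.77, and 2[1 − Φ(1.96/√1.77)] ≈ 14%. Simulated values for n = 20:

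| τ²/σ² | 0 | 0.25 | 0.5 | 1.0 |
|---|---|---|---|---|
| 4 samples | 5.0% | 13.9% | 20.3% | 27.7% |
| 10 samples | 5.0% | 26.6% | 37.1% | 47.2% |

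With n = 6 the range is 14.3% to 49.0%.

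**5. Type I error, carry-over kept as listed.** Mean, period, treatment and carry-over use up the four sequence-by-period means, so treatment is estimated from period 1 alone, between infants. The true variance per infant is ω² + τ² + σ²/m. The model estimates it by (MSB + MSW)/2m, where E(MSB) = L + 2mω² and MSW is the mean square in step 4.

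Example: n = 20, m = 10, τ² = 1, ω² = 0.5. The true value is 1.60. The estimated value is (21 + 1.48)/20 = 1.12. The ratio is 1.42, giving about 10%.

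Over τ² = 0.25 to 1.0 and ω² = 0.5 to 2, simulation at n = 20 gave 5.5% to 9.7% with Satterthwaite degrees of freedom. Residual degrees of freedom give up to about 12%.

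**6. One summary per infant-day.** Averaging the samples after 0 h and testing the crossover differences gave 4.4% to 5.4% type I error in the settings simulated, with no dilution.

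**The case against.** A reader might infer that the plan codes the 0-h sample as treated and takes serial samples as independent, so that p-values are certain to be far too small. The documents do not support that.

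- The quoted clause explains why mixed models suit a crossover. It is not a complete model statement, and the remark about covariance leaves room for a correct structure.
- Section 3.5.4 separately mentions describing baseline measures, so treating 0 h as a baseline is a natural reading.
- The fallback tests in section 3.5.4 work on subject totals and on period and crossover differences. These presuppose one value per infant-period.
- The large error rates belong to a model without carry-over, a term the plan lists. With it kept, inflation is modest, and at zero day variance there is none.
- Dilution and inflation pull in opposite directions. With n = 20, four samples, no day variance and a true effect of 0.60, the all-samples model had 79% power against 87% for the daily summary.
- Under section 2.1, plasma glucose is a single 1-h value, with neither dilution nor replication.
- The stated mechanism is lower insulin and higher glucagon. Restored ketones are not part of it.
- The sample size "is a sample of convenience and not based on statistical considerations", and GIR is untouched.

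All of this stands, and it limits the point to missing specification with conditional consequences. It does not close the gap: permitting a structure is not choosing one, and nothing says how four or ten samples become the one value the fallback tests need.

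**Conclusion.** The point holds as under-specification of the insulin and betahydroxybutyrate analyses. If all samples are entered with the listed terms, a constant effect during the infusion is diluted by 25% for insulin and by 10% for betahydroxybutyrate (given ten values from 0 to 9 h). This needs no variance assumption.

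Inflated type I error is conditional on a shared day effect. For infant-by-day variance of 0.25 to 1.0 times residual it is about 6-10% with carry-over kept and about 14-49% with it dropped; at zero it stays at 5%. The documents supply no value for that variance.

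Plasma glucose is exposed only if the 1-h definition in section 2.1 is not the one analysed. The primary GIR analysis is unaffected. The change should be made, but the primary conclusion does not depend on it.

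**What to change.** In section 3.5.4, for insulin and betahydroxybutyrate:

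1. Take as response only samples after 0 h and up to 9 h, and use the same day's 0-h value as a covariate. This also settles that the later samples from infants off dextrose stay out of the comparison.
2. Then choose one route in advance. Either reduce each infant-day to one stated summary (for insulin, for example, the mean of the 1, 5 and 9 h values) and apply the GIR model, or keep the serial values and add time, treatment-by-time and a random infant-by-day effect.
3. Reconcile section 2.1 (plasma glucose at 1 h) with section 3.4 item 14 and sections 3.5.2 and 3.5.4, so that one definition of the glucose outcome is analysed.

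The cost is a few sentences of SAP wording and somewhat wider intervals where a day effect exists. The 0-h values are already collected, so no sampling or procedure changes.

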Pharmacokinetics: Exendin-(9-39) plasma concentration-time data will be analyzed using a moment-based, non-compartmental approach (NCA) with WinNonlin (version 5.1, Pharsight Corporation). Basic PK metrics including C_{max} , C_{eoi} , T_{max} , and $AUC_{0-\infty}$, and AUC_{0-t} will be calculated in addition to derived parameters such as elimination half-life. A model-based approach will be utilized in parallel to describe the individual pharmacokinetic parameters including exendin-(9-39) clearance (CL) and volume of distribution (VD) once the appropriate structural model (e.g., one or two-compartment) has been determined. Sources of variability will be described and the contribution of patient-specific covariates to explain sources of variation will be examined via a rigorous covariate analysis using nonlinear mixed effect modeling and the NONMEM (version 6) algorithm. Briefly, covariates will be included in the model if deemed significant ($p < 0.05$) observed as a reduction in the objective function value (OFV) greater than 3.84 (χ^2 distribution, $df=1$). Subsequently, covariates will be retained in the model if fixing their value to zero results in greater than 10.84 (χ^2 distribution, $df=1$) increase in the OFV, at a higher level of stringency ($p < 0.001$). Ultimately, the final model will be selected using a combination of goodness-of-fit criteria including diagnostic scatter plots, convergence with at least 3 significant digits, reasonable parameter estimates and precision of parameter estimates. Diagnostic plots of the base model will evaluate the correlation between PK parameters (clearance, volume) with indices of body size (e.g., bodyweight) and, if so, an allometric model will be considered during model development. The underlying basis for this type of model has been previously described as useful in pediatrics in that it incorporates known physiologic relationships in the covariate-parameter model (93). The effects of categorical covariates will be modeled using normalized power model.

Safety: Summary statistics and plots will be generated for the change from baseline values in the vital signs, ECG parameters, and selected laboratory safety parameters, as deemed clinically appropriate. Depending on the safety parameter,

the difference from baseline will either be computed on the original scale (raw change from baseline) or on the log scale and back-transformed for reporting (percent change from baseline). Summary statistics for the raw laboratory safety tests, ECGs, and/or vital signs may also be computed, as deemed clinically appropriate.

4. Subject Selection and Withdrawal

4.1. Inclusion and Exclusion Criteria

Inclusion Criteria:

- Confirmed diagnosis of congenital hyperinsulinism (based on clinical criteria: insulin, beta hydroxybutyrate, and/or free fatty acid plasma levels at the time of hypoglycemia, and/or glycemic response to glucagon at the time of hypoglycemia)
- Age: from birth to 12 months
- Failure to respond to diazoxide (defined as the failure to maintain blood glucose ≥ 70 mg/dL without supraphysiologic rates of glucose infusion: > 4-5 mg/Kg/min)

Exclusion Criteria:

- Evidence of a medical condition that might alter results, including active infection, kidney failure, severe liver dysfunction, severe respiratory or cardiac failure
- Current therapy at the time of initiation of study procedures with medications that affect glucose metabolism, such as high dose glucocorticoids, β -agonists, glucagon, diazoxide and octreotide. Subjects will be eligible to participate 4 hours after glucagon discontinuation, 24 hours after the last dose of octreotide and 72 hours after last dose of diazoxide
- Subjects with suspected Beckwith-Wiedemann syndrome or other syndromic forms of congenital hyperinsulinism

4.2. Rationale for Using Neonates and Children

Congenital hyperinsulinism is a genetic disorder of insulin regulation, most commonly due to mutations in the K_{ATP} channel. Affected individuals present shortly after birth with severe hypoglycemia and require high glucose infusion rates through a central line to maintain safe blood glucose levels, as they are unresponsive to available medical therapy. The majority of these children require a near-total pancreatectomy to ameliorate the hypoglycemia. Approximately 50% of these children will require some medical intervention (frequent or continuous enteral feedings and/or octreotide) after surgery. The severity of the disorder seems to ameliorate with age, as many of the affected adult individuals who did not undergo a pancreatectomy as infants followed by our team have a safe fasting tolerance. Therefore, it is important to perform these studies in the

population more severely affected: infants and children. Studying the effect of the GLP-1 receptor antagonist, exendin-(9-39), on glucose metabolism of these subject population will provide information that can be used to improve their management and in the developing of new therapies.

4.3. Subject Recruitment

Subjects will be recruited from the Hyperinsulinism Center at The Children's Hospital of Philadelphia, the largest center in this country caring for children with disorders of insulin regulation. Every year our center treats approximately 30 children with medically unresponsive hyperinsulinism that require pancreatectomy. Currently we have approximately 1200 in-patient days a year. This put us in a unique position to conduct research directed to develop new therapies for this disorder.

The study will be advertised in the center's website. Additional study information will be posted to the Pediatric Endocrine Society (PES) website. This web page lists clinical research studies that are recruiting pediatric endocrine subjects across the United States and Canada. The purpose of the web page is to inform the pediatric endocrinology community about clinical research studies, and to allow providers and patients/families to identify clinical research studies that may be of interest. Access to the page is unrestricted.

4.4. Early Withdrawal of Subjects

4.4.1. When and How to Withdraw Subjects

Subjects will be withdrawn from the study if the test of hypersensitivity is positive upon admission before the initiation of the study protocol. Subjects will be withdrawn at any time during the study if an unexpected severe adverse event occurs. There are not expected safety concerns for abrupt termination of the study protocol.

4.4.2. Data Collection and Follow-up for Withdrawn Subjects

In the event of withdrawal before completion of the study protocol, data obtained until the time of withdrawal will be collected and used in the final analysis.

5. Safety and Adverse Events

5.1. Definitions

Adverse Event

An **adverse event** (AE) is any symptom, sign, illness or experience that develops or worsens in severity during the course of the study. Intercurrent illnesses or

injuries will be regarded as adverse events. Abnormal results of diagnostic procedures will be considered to be adverse events if the abnormality:

- results in study withdrawal
- is associated with a serious adverse event
- is associated with clinical signs or symptoms
- leads to additional treatment or to further diagnostic tests
- is considered by the investigator to be of clinical significance

Serious Adverse Event

Adverse events will be classified as serious or non-serious. A ***serious adverse event*** is any AE that is:

- fatal
- life-threatening
- requires or prolongs hospital stay
- results in persistent or significant disability or incapacity
- a congenital anomaly or birth defect
- an important medical event

Important medical events are those that may not be immediately life threatening, but are clearly of major clinical significance. They may jeopardize the subject, and may require intervention to prevent one of the other serious outcomes noted above. For example, drug overdose or abuse, a seizure that did not result in in-patient hospitalization, or intensive treatment of bronchospasm in an emergency department would typically be considered serious.

All adverse events that do not meet any of the criteria for serious should be regarded as ***non-serious adverse events***.

Adverse Event Reporting Period

The study period during which adverse events must be reported is normally defined as the period from the initiation of any study procedures to the end of the study treatment follow-up. For this study, the study treatment follow-up is defined by the half-life of the drug and will be 24 hrs after the end of infusion.

Preexisting Condition

A preexisting condition is one that is present at the start of the study. A preexisting condition will be recorded as an adverse event if the frequency, intensity, or the character of the condition worsens during the study period.

General Physical Examination Findings

At screening, any clinically significant abnormality will be recorded as a preexisting condition. At the end of the study, any new clinically significant findings/abnormalities that meet the definition of an adverse event will also be recorded and documented as an adverse event.

Post-study Adverse Event

All unresolved adverse events will be followed by the investigator until the events are resolved, the subject is lost to follow-up, or the adverse event is otherwise explained. At the last scheduled visit, the investigator will instruct each subject to

report any subsequent event(s) that the subject, or the subject's personal physician, believes might reasonably be related to participation in this study. The investigator will notify the IRB, CTRC, and the FDA (per the IND) of any death or adverse event occurring at any time after a subject has discontinued or terminated study participation that may reasonably be related to this study. These agencies will also be notified if the investigator should become aware of the development of cancer or of a congenital anomaly in a subsequently conceived offspring of a subject that has participated in this study.

Abnormal Laboratory Values

A laboratory test abnormality considered clinically relevant by the investigator (e.g. the abnormality suggests a disease and/or organ toxicity, or is of a degree that requires active management such as change of dose, discontinuation of the drug, more frequent follow-up assessments, or further diagnostic investigation) should be documented as an adverse event.

Hospitalization, Prolonged Hospitalization or Surgery

Any adverse event that results in hospitalization or prolonged hospitalization will be documented and reported as a serious adverse event unless specifically instructed otherwise in this protocol. Any condition responsible for surgery will be documented as an adverse event if the condition meets the criteria for and adverse event.

Neither the condition, hospitalization, prolonged hospitalization, nor surgery will be reported as an adverse event in the following circumstances:

- Hospitalization or prolonged hospitalization for diagnostic or elective surgical procedures for a preexisting condition. Surgery will **not** be reported as an outcome of an adverse event if the purpose of the surgery was elective or diagnostic and the outcome was uneventful.
- Hospitalization or prolonged hospitalization required to allow efficacy measurement for the study.
- Hospitalization or prolonged hospitalization for therapy of the target disease of the study, unless it is a worsening or increase in frequency of hospital admissions as judged by the clinical investigator.

